**Clinical Investigation of the VR-800 Device:
Statistical Methods and Analytic Considerations**

NCT Number: NCT04208750

Document Date: 03 FEB 2020

Statistical methods and analytic considerations

Sample size. An initial calculation was made for the continuous subjective rating data to determine the sample size required to detect an expected small effect size (0.3) using a paired samples-t-test targeting 80% power and level of significance of 5% (two-sided). This calculation indicated that a total sample size $N=90$ was required to detect an effect size of 0.3 in the paired mean difference between the Vision-R™ 800 and the standard refractions. Because several of our subjective measures were based on a comparison of proportions in the full sample ($N=90$) we also estimated the sample size needed for testing a difference in proportions of $\Delta p = 0.65 - 0.35 = 0.3$ in a paired-sample design. We found that the required sample size of $N=85$ would achieve 80% power at the two-sided 5% level of significance.

To allow for an attrition rate of 25%, we increased the larger of the two sample size estimates ($N=90$) to obtain a post-screening study sample size of $N=120$.

Overview. All analyses were performed using R v3.5.3 (The R Foundation; www.r-project.org) and SAS v9.4 (SAS Institute, Cary, NC, USA). For each outcome measure, all available data were incorporated into the statistical analyses and modeling. Although not a primary comparison, habitual lens information is included in some instances to provide additional context for comparison of the Vision-R™ 800 and standard refraction technologies data.

Refractive error. Clinically obtained measures of refractive error measures (sphere, cylinder and axis) were converted to Cartesian power vector coordinates (M, J0, and J45)(Thibos, Wheeler et al. 1997, Thibos and Horner 2001) and refractive error differences depicted graphically in three-dimensional plots, conditioned by both refraction technology and participant group. These data were summarized in terms of parameter estimates of location (i.e., mean and median) and dispersion (i.e., standard deviation, standard error of the mean, median, minimum, maximum, range and 95% confidence intervals based on quantiles of the Student's *t*-distribution). Multivariate tests were used to statistically evaluate hypotheses related to differences between the refraction technologies.

LogMAR visual acuity. Sample distributions of logMAR visual acuity for each refraction method conditioned by participant group and viewing distance were depicted graphically using box-and-whisker plots and analyzed using linear mixed-effects (LME) regression. Separate models were fit to the near and distance data by restricted maximum likelihood estimation. Each LME model included fixed-effects terms for refraction method, participant group, and the refraction x participant group interaction as well as participant-specific random intercepts.

Subjective preferences and rating-scale data. All categorical measures were summarized and depicted graphically in terms of percentages of participants endorsing each response category. For descriptive purposes, we report both a point estimate for each response percentage along with a 95% confidence interval to quantify the precision of the estimate. Bayesian methods were used to obtain estimates of [1] the relative frequency of participants' preferences for, confidence in, and perceived benefits of the Vision-R™ 800 refraction technology and [2] the Bayes factor that quantifies the relative probability of the observed data under two competing models (e.g., null and alternative hypotheses). Friedman rank sum tests with pairwise post-hoc tests were used to analyze symptom frequency ratings for habitual, Vision-R™ 800, and standard glasses.

Missingness due to COVID-19. There were two main data-related issues in this study due to the COVID-19 global pandemic and subsequent lockdown that began while the study was underway. First, because the pandemic prevented many participants from attending their final in-office visit, final subjective questionnaire responses were collected for some participants using an electronic survey. Post-hoc analyses indicated no significant differences between measures collected in-office and those collected remotely. Thus, all in-office and remotely collected data were pooled for purposes of analysis. Second, we note that differences in the final sample size of the two study groups (N=49 versus N=39 for young adults and presbyopes, respectively) are related to recruitment process at the beginning of the study rather differential drop-out during the study. Third, statistical comparisons between response proportions for the refraction technologies in the full sample remains appropriately powered. However, for conditional analyses comparing refraction methods within the young adult and presbyope subgroups, some caution is advised as the implied power is slightly under the targeted level of 80% for intermediate effect sizes.

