- Quantify the reliability, repeatability, and efficiency of the Vision-R800 phoropter
- Subjectively and objectively compare the refraction experience for the optometrist with the Vision-R800 phoropter as compared to a traditional refraction, from training through prescription writing
- Subjectively and objectively compare the refraction experience for the patient with the Vision-R800 phoropter as compared to a traditional refraction.
- Quantify the value of high precision glasses, in terms of subjective and objective optical performance.

STUDY DESIGN:

This study is a randomized, bilateral, cross-over dispensing study of the full patient experience/process as would occur in the private practice setting, including the refraction and spectacle dispensing. Specifically, “patient” subjects are randomized to experience the traditional refraction and glasses dispensing (0.25D step lenses) or the Vision-R800 refraction and precision glasses (0.01D step lenses). Patient expectation and experience will be gathered prior to, during, and following the experience and lens use. The doctors will be part of the team of investigators. This investigation will run concurrently to phases one and three.

Vision-R800 Machine Details:

The Vision-R800 phoropter systems have been installed in two 4meter exam lanes at the IU School of Optometry.

For all phases of the study, the optometrists will be asked to refract using the “Smart Exam” algorithm with a few minor modifications. First, steps 14 and 15 (binocular vision and stereo) will be removed.

For presbyopes, following testing of distance visual acuity, the algorithm will test JCC and near visual acuity with the add after all of the above distance testing.

Following the refraction, the prescription will be converted from 4 meter testing to infinity using the Vision-R800 conversion equation.

CONFIDENTIAL

Evaluation of Patient Experience (IU experienced doctors refract naive subjects in a crossover dispensing):

Phase two will consist of a new group of naïve patients. A total of 120 patients will be grouped into single vision and progressive addition wearers. Sixty subjects will be included in each of the single vision and presbyopic lens categories, with 30 trying the traditional refraction process and lenses first and 30 trying the new refraction process and lenses first.

1. Young adults: 19-35 years of age
2. Presbyopic adults: 36-80 years of age, progressive addition lens wearers

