Following informed consent, the patient will be asked demographic and other subjective/baseline questions about their past experience with refraction and glasses dispensing(s), as well as expectations. These may be video recorded verbal conversations or paper questionnaires. Subjects may be given a wearable heart rate monitor for the remainder of the procedures.

Patients will be randomized to experience either a traditional refraction or a Vision-R800 refraction performed by a study team member (optometrist). The starting point will be the patient's habitual prescription. The refraction will be audio/video-recorded. A final prescription will be generated. Following the refraction, subjective feedback will be obtained.

Patients will be presented with a frame board (of standard, Luxotica frames) and asked to choose a frame. The necessary fitting measurements and adjustments will be made. Spectacle lenses will be manufactured for this frame using prescriptions from either the traditional refraction or the Vision-R800 refraction.

Upon arrival and verification of the edged and assembled glasses, patients will be presented with their spectacles. Spectacles will be dispensed by an experienced optician. At dispensing and at a two-week follow-up visit, subjective and objective vision testing will be completed. Subjects will be asked to wear their glasses at least 6 hours per day.

Subjects will then be randomized to the other type of refraction and all testing procedures will be repeated. All frames and lenses will be provided by the Sponsor. Between the ordering of the second pair of glasses and their dispensing, subjects will be asked to wear their habitual spectacles.

At the final visit, an investigator will show the patient the following prescriptions, in a randomized order, via the Vision-R800 phoropter, and record visual acuity and subjective ratings, while keeping the patient masked. Finally, the patient will be asked their preference for each prescription in paired comparisons, both monocularly and binocularly.

1. Habitual glasses prescription
2. Traditional refraction prescription
3. Vision-R800 refraction prescription

Primary Outcome Measures:

- Test potential claims with patients, as measured by subjective questionnaires
- Assess the benefits of the full Vision-R800 experience from refraction to lenses to the patient, as measured by subjective questionnaires

Other Outcome Measures:

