- Vision quality assessments with traditional refraction and Vision-R800 refraction, as measured by visual acuity and subjective vision ratings

Participants:**Enroll up to 128 to finish 120 subjects, equally split into the below groups:**

Young adults: 18+ years of age, single vision glasses wearers

Presbyopic adults: 40-70 years of age, progressive addition lens wearers

*each arm will be targeted to be age, sex and spherical Rx matched, although this is not a requirement

Other subject criteria include:

Not have taken part in other phases of this study

Free of eye disease with an impact on visual acuity or binocular vision abnormalities (by self-report)

The Presbyopic adults must be current adapted progressive addition lens wearers, and the other subject age groups must not be wearing progressive addition lenses.

No formal training in optometry, vision science or in the eyecare field

Must have a wearable pair of glasses from a prescription \leq 2 years old

Must wear glasses at least six hours per day over the last two weeks, and willing to continue wearing glasses at least six hours per day throughout the study

OUTCOME MEASURES:

To achieve the aims outlined above, the outcome measures for this study are broken down into four groups based on where the data is obtained: Patients, Optometrists, Vision-R800 Phoropter and the Glasses.

PATIENTS:**BACKGROUND:**

- Personality Type/attention to detail
- Early adopter to technology (type/age of cell phone?)
 - Would your friends describe you as tech savvy (likert)
- Last eye exam, exam experience
- Age of habitual glasses and where they were purchased
- Current satisfaction with habitual glasses prescription
- Pre-exam expectations
- Habitual prescription including pupillary distance (via lensometry)

DURING REFRACTION:

- Stress/comfort (heart rate, subjective questions, observations from video)
- Casual conversation (observations from the video)
- Step-size of refraction, as calculated by algorithm

AFTER REFRACTION:

- Subjective feedback
 - Overall satisfaction with refraction; likes and dislikes
 - Was there any sort of learning curve with how to respond?
 - Stress level/comfort during refraction
 - How does this compare to what you've had done in the past?
 - Level of confidence with prescription (5-point likert), comments
 - Quality of the refraction (5-point likert), comments
 - Likelihood to purchase glasses from refraction (5-point likert), comments (*following both refractions*)

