 - Subjective preference (traditional refraction, Vision-R800 refraction)
 - Overall satisfaction with refraction (5-point likert), comments
 - Stress level/comfort during refraction (5-point likert), comments
 - Level of confidence with prescription (5-point likert), comments
 - Quality of refraction (5-point likert), comments
 - Do you feel the Vision-R800 refraction provides better eyecare? (5-point likert), comments
 - Would you seek out an optometrist with this technology? (5-point likert), comments
 - Do you feel that the lenses manufactured from this technology would be more valuable? (5-point likert), comments

- Did the introduction to this concept live up to your expectations?
- Did you like the technology the doctor had?
- Overall, did you prefer one experience overall?
- Perception of the field of view (no question will be asked about this, and it will not be mentioned; instead it will be noted if this is mentioned in the comments from the participant)
- Monocular and binocular preference between Habitual Rx, traditional refraction endpoint, Vision-R800 refraction endpoint (done by investigator, with subject remaining masked to prescriptions)
- Agreement of quality observed in simulation inside Vision-R800 phoropter versus outside world

VISION-R800 PHOROPTER:

- Final prescription given (traditional refraction vs. Vision-R800 refraction algorithm endpoint and doctor's endpoint)
 - Visual acuity with prescriptions
 - Quality of vision with prescriptions
 - Preference with prescriptions
- Repeatability
 - Within doctor (repeatability of endpoint)
 - Between doctor
 - Improvement with number of refractions completed?
- Path of refraction (what lens choices were given)
- Sensitivity of subject to lens changes (0.25D vs 0.01D)
- Efficiency of algorithm (how many questions were asked)
- Length (time)
- Education level required to do the refraction
- Objective refractions versus subjective refractions

GLASSES:

AT DISPENSING AND FOLLOW UP:

- High Illumination, high contrast logMAR Visual Acuity
- Subjective Questionnaires
 - Quality of vision ratings
 - Glare ratings
 - Halos ratings
 - Ghosting ratings
 - Preference compared to habitual lenses (or control lenses)
- Agreement of quality observed in simulation inside instrument versus outside world

STATISTICAL ANALYSIS:

Repeated measures ANOVA and mixed effects regression models will be used to analyze both the main and interaction effects of outcome measures

PUBLICATION PLAN:

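### The logMAR acuity mixed model for this two-order crossover has no period term; if the acuities come from the two periods, it loses some precision and has no protection against unequal orders

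*SAP*

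**What the plan says.** **Design.** The protocol (*Study Design* and *Evaluation of Patient Experience*) describes a randomised crossover with sixty subjects in each lens category, "with 30 trying the traditional refraction process and lenses first and 30 trying the new refraction process and lenses first". All testing is repeated after the switch.

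**Model.** The SAP (*LogMAR visual acuity*) fits separate near and distance models by REML: "Each LME model included fixed-effects terms for refraction method, participant group, and the refraction x participant group interaction as well as participant-specific random intercepts". No period, sequence or visit term is listed. The protocol's *Statistical Analysis* section names only repeated measures ANOVA and mixed models.

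**Which acuities.** The SAP does not say. The protocol offers these candidates:

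- *Glasses, at dispensing and follow up*: "High Illumination, high contrast logMAR Visual Acuity". The timing is given under the visits: "At dispensing and at a two-week follow-up visit, subjective and objective vision testing will be completed". This happens once per period, and it is the only place where the protocol uses the word logMAR.
- The final visit, where three prescriptions are shown "in a randomized order, via the Vision-R800 phoropter, and record visual acuity and subjective ratings, while keeping the patient masked". This is one sitting after both periods.
- *Vision-R800 Phoropter*: "Visual acuity with prescriptions", with no visit attached. It stands beside quality and preference, much like the content of the final visit.

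**Status.** Acuity falls under *Other Outcome Measures*: "Vision quality assessments with traditional refraction and Vision-R800 refraction, as measured by visual acuity and subjective vision ratings".

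**The concern.** In a two-period crossover, each participant's Vision-R800 minus standard difference contains the method effect plus or minus the period effect. The sign depends on the order received. Acuity could drift between periods through practice with the chart, familiarity with testing, or the calendar. The listed model has no term to absorb such a drift.

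Two things follow. With equal orders the signs cancel in the mean but widen the spread of the differences, so the standard error is larger than the design requires. With unequal orders the signs do not cancel fully, and part of the period effect enters the method estimate. The planned 30/30 split guards against the second problem. The analysed sample, however, is 88 (49 young adults, 39 presbyopes) rather than 120, and its split by order is not reported.

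**Working it through.** **The plan's own figure.** The SAP's sample size is for subjective ratings: paired t-test, effect size 0.3, 80% power, two-sided 5%. The noncentral t gives N = 90 (power 80.4%), and 90 / (1 − 0.25) = 120. Both reproduce. At N = 88 the same calculation gives 79.5%. The SAP makes no power claim for acuity, so 0.3 serves below only as a yardstick.

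**Inputs.** From the documents: two orders, the listed model terms, and groups of 49 and 39 (N = 88). Assumed, because the documents give no period effect, acuity SD or split by order: a period shift π in SDs of the paired difference, and the order splits n1/n2.

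**Set-up.** With one value per method and complete pairs, the random-intercept model tests method in the same way as a regression of the paired difference D on an intercept and group. Within order, D = δ ± π + error, with error SD 1.

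**Balanced orders.** The bias is 0. Without a period term the variance of D is about 1 + π², so the standard error grows by √(1 + π²): 1.005 at π = 0.1, 1.020 at 0.2, 1.044 at 0.3 and 1.118 at 0.5. Simulated power at 44/44, δ = 0.3, group term fitted (the spread reflects separate simulation runs):

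| Shift π | Without period | With period | Loss (points) |
|---|---|---|---|
| 0.1 | 78.6% | 78.9% | about 0.3 |
| 0.2 | 77.6% | 79.0% | about 1.4 |
| 0.3 | 76.0% to 77.0% | about 79% | about 3 |
| 0.5 | 71.1% to 72.1% | about 79% | about 7 to 8 |

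Type I error without period is about 4.1% at shift 0.3 and 2.8% at 0.5, so the test is conservative. With period it is about 5%.

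**Unequal orders.** Bias = π × (n1 − n2) / N.

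- 48/40: 0.3 × 8/88 = 0.027 SD; 0.5 × 8/88 = 0.045 SD. Type I error is 4.8% or 4.2%.
- 52/36: 0.3 × 16/88 = 0.054 SD (0.0545 before rounding); 0.5 × 16/88 = 0.091 SD. Type I error is about 6.7% or 9%.

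With a period term the bias is 0 and type I error about 5% in each case.

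**Second-period records missing.** The SAP uses all available data, so a participant who lacks only the second-period value still contributes the first. Starting from 44/44, with an assumed participant-to-residual variance ratio of 1 to 4, the bias is 0 if losses are equal by order. It is 4% to 5% of the shift if 20 records are lost 12/8, which at shift 0.3 is at most 0.3 × 0.05 = 0.015 SD.

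**More than one record per method.** If two visits are stacked with only a participant intercept, type I error is 6.4% to 14.8% for assumed glasses-to-residual variance ratios of 0.1 to 1, with no period or visit shifts. Entering two eyes gives a similar 6.7% to 14.6% for participant-by-method ratios over the same range.

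**The case against.** **The records may not be period-based.** If the masked final-visit acuities were modelled, treatment period does not apply, and the point reduces to an omitted presentation-order term. This stands as a condition. The wording favours the dispensing and follow-up records but does not settle it. The near-acuity step in *Vision-R800 Machine Details*, "the algorithm will test JCC and near visual acuity with the add after all of the above distance testing", does not help: it belongs to the Vision-R800 algorithm and to presbyopes, so alone it cannot supply a near model that compares both methods in both groups.

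**The effect may be negligible.** Nothing in the documents suggests a sizeable period shift in acuity. At shifts of 0.1 to 0.2 the loss is at most about 1.5 points, and the larger losses come from the upper part of the assumed range. This also stands.

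**A reader might infer that the acuity comparison is biased.** The documents do not support that. The planned orders are equal, and nothing shows that the analysed orders are not. The SAP (*Missingness due to COVID-19*) says many participants missed the final in-office visit and describes the electronic survey only for questionnaires, so some acuity may be missing. But second-period refraction and dispensing precede the two-week visit, and equal losses by order give no bias. The unequal splits above are illustrations.

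**A reader might also infer that standard errors are too small.** That requires more than one record per method per participant. The study is bilateral and has two visits per period, so this is possible, but the SAP's plots by method, group and distance fit one value per method equally well.

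**Conclusion.** The point holds in a limited form. The model lists no period term in a two-order crossover. If the modelled acuities come from the two periods, which is the natural reading, any period effect inflates the residual. Under balance the cost is sensitivity alone: from almost nothing at a shift of 0.1 to about 7 to 8 power points at 0.5, on a borrowed effect size. Bias is conditional on an unreported imbalance and is modest in the splits examined. The severity is minor, because acuity is a non-primary outcome and the primary questionnaire outcomes are untouched. The shifts, the splits and the use of 0.3 for acuity are all assumptions.

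**What to change.** 1. State which acuity records entered the near and distance models, and report analysed participants by order within each group.
2. If the records come from the two periods, refit both models with period as a fixed effect for the Vision-R800 versus standard comparison. Leave habitual-lens records out of that model, since they belong to neither period. Label the refit post hoc, because the SAP reports models already fitted.
3. If the masked final-visit acuities were used, add presentation order instead.
4. If more than one record per method per participant is entered (two visits or two eyes), also add a participant-by-method random effect, and a visit fixed effect where visits are stacked. This may give a larger standard error and p-value.

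**Cost.** A short re-run, provided order is in the dataset. The period term takes one degree of freedom. With no true period effect there is no power loss at 44/44 and about one point at 52/36 (78.8% to 77.6%). A period term does not remove carryover.

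### If readings from both visits enter the logMAR acuity model, a participant intercept alone can understate the standard error of the refraction-method effect

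*SAP*

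**What the plan says.** **Measurements planned.** For each pair of glasses, the protocol (Evaluation of Patient Experience) states: "At dispensing and at a two-week follow-up visit, subjective and objective vision testing will be completed". In its Outcome Measures section, the Glasses list for dispensing and follow-up begins with "High Illumination, high contrast logMAR Visual Acuity". That gives two planned logMAR readings per participant per refraction method. A further acuity record is planned at the final visit, when the habitual, traditional and Vision-R800 prescriptions are shown "via the Vision-R800 phoropter, and record visual acuity and subjective ratings, while keeping the patient masked".

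**Data used.** The SAP Overview says: "For each outcome measure, all available data were incorporated into the statistical analyses and modeling".

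**Model.** The SAP paragraph on logMAR visual acuity says: "Separate models were fit to the near and distance data by restricted maximum likelihood estimation". The terms are refraction method, participant group, "the refraction x participant group interaction as well as participant-specific random intercepts". It lists no visit, period or sequence term and no participant-by-method (pair) term. It does not say which visit's acuity was modelled, whether two visits were stacked or averaged, or whether acuity was taken through the glasses or the phoropter.

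**Status of the outcome.** The protocol puts visual acuity under Other Outcome Measures. The primary outcomes are questionnaires.

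**The concern.** A participant random intercept gives every two readings from one person the same correlation, whether they were taken through the same pair or through different pairs. Two readings through the same pair also share whatever is specific to that person's prescription and lenses. This participant-by-method variation is the error term for comparing methods, because a second reading through the same pair does not average it away. If both visits are rows and the model has no such term, it treats the second reading as more new information than it is.

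At stake are the confidence interval and p-value for Vision-R800 versus standard acuity, and those for the method-by-group interaction. Both could be too optimistic for the objective vision measure in a device comparison. Modelling near and distance separately does not help, since the repeat lies within each distance.

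**Working it through.** **The plan's own figure.** The only power figure for a continuous measure is for subjective ratings: "a total sample size $N=90$ was required to detect an effect size of 0.3 in the paired mean difference". It reproduces: an exact paired t-test at two-sided 5% gives N = 90 with 80.4% power, and 90/(1 − 0.25) = 120. It has no bearing on the acuity model, for which the SAP gives no precision or variance figures.

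**Inputs.**
- N = 88, from 49 young adults plus 39 presbyopes (SAP, Missingness due to COVID-19).
- Two methods, and two readings per method if both visits are used (protocol).
- r = participant-by-method variance divided by residual variance. The documents give no value, so r is an assumption and a range is shown.
- Complete data at both visits for both pairs, also an assumption. Missing readings would reduce the effect, because a pair read only once has no repeat to miscount.

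**True variance.** In units of residual variance, the difference between a participant's two method means has variance 2(r + 1/2) = 1 + 2r. The method effect therefore has variance (1 + 2r)/N.

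**Variance the model reports.** The intercept-only model replaces (1 + 2r) with the pooled within-participant mean square. This combines N − 2 = 86 degrees of freedom with expectation 1 + 2r and 2N = 176 with expectation 1:

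pooled = [86(1 + 2r) + 176] / 262

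Model SE / true SE = √[pooled / (1 + 2r)], and real error = 2[1 − Φ(1.96 × ratio)].

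Example, r = 0.5: pooled = (172 + 176)/262 = 1.328; ratio = √(1.328/2) = 0.815; 1.96 × 0.815 = 1.597; error 11.0%.

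| r (assumed) | pooled | 1 + 2r | model SE / true SE | real error at nominal 5% |
|---|---|---|---|---|
| 0 | 1.000 | 1.0 | 1.00 | 5.0% |
| 0.1 | 1.066 | 1.2 | 0.94 | 6.5% |
| 0.25 | 1.164 | 1.5 | 0.88 | 8.4% |
| 0.5 | 1.328 | 2.0 | 0.82 | 11.0% |
| 1 | 1.656 | 3.0 | 0.74 | 14.5% |

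The same ratio applies to the method-by-group interaction, which is tested against the same pooled variance.

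**Simulation check.** In 20,000 simulated trials per setting, using the balanced-data equivalent of the mixed model, the error was 5.1%, 8.2%, 11.1% and 14.6% at r = 0, 0.25, 0.5 and 1. With one reading per participant per method it stayed between 5.1% and 5.4% at all four values.

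**Visit shift.** If mean acuity moves by d residual standard deviations between visits and there is no visit term, N·d² is added to the numerator of the pooled variance. At d = 1 the numerator gains 88, and the SE ratio becomes 1.16, 1.00, 0.91 and 0.82 at r = 0, 0.25, 0.5 and 1. The missing visit term therefore pushes the reported standard error upward, against the missing pair term.

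**The case against.** The strongest reply is that the SAP never says both visits were modelled. Its acuity plots are described by method, group and viewing distance, and visit appears in neither plots nor model. That fits one reading per method and distance, for which a participant intercept is the right paired analysis. The Overview sentence is general and may mean only that incomplete participants were kept. The acuity might also come from the phoropter: the SAP paragraph speaks of refraction method rather than glasses, and the protocol mentions near acuity explicitly only in the refraction algorithm.

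Much of this stands, and it is why the point is conditional. It does not remove the point. The protocol names logMAR acuity as a planned measurement only in the Glasses list for dispensing and follow-up. Using one visit would leave planned readings out, and nothing in the SAP says that this was done.

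A reader might infer three stronger things, none of which the documents support:
- **That the reported standard error is definitely too small.** This needs both visits as rows, pair-level variance above zero, and no visit shift large enough to cancel it. None of these can be checked from the text.
- **That right-eye, left-eye and binocular acuities were also stacked.** The protocol's monocular and binocular wording concerns preference, not logMAR acuity through the glasses.
- **That missed final visits during lockdown biased the method comparison.** Those visits fall in the second period, but order was randomised with 30 per sequence planned in each group. The losses should therefore fall about equally on both methods.

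**Conclusion.** The point holds conditionally. On the literal reading of the two documents, the acuity model takes two readings per pair and lacks the term that recognises their shared variation. The real error of a nominal 5% test is then about 6.5% to 14.5% for assumed variance ratios of 0.1 to 1, and 5% if the ratio is zero. These figures assume 88 participants with complete data and no visit shift. A shift of one residual standard deviation would cancel the understatement at a ratio of 0.25 and leave part of it at 0.5 and 1; correct coverage reached that way would be accidental.

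If one reading per participant per method was used, the model is sound and only a sentence saying so is missing. The consequence is confined to acuity, among the other outcome measures. The primary questionnaire outcomes do not use this model. The change should be made, but it does not threaten the trial's main conclusions.

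**What to change.** State in the SAP which acuity readings (visit and source) feed the near and distance models. Then do one of the following:

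1. **If both visits are used:** add a participant-by-method (pair) random intercept and a fixed visit term (dispensing, two weeks) to both models. This handles both the pair-level correlation and any visit shift.
2. **Otherwise:** analyse one reading per participant per pair, either the two-week value or the mean of the two visits, and keep the participant intercept. A pair intercept should not be added here, because it cannot be separated from residual error. If the mean is chosen, say how a pair with only one visit is handled.

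The cost is one SAP sentence, one or two model terms and a refit. The acuity interval may widen. Using only the two-week value would also lose acuity for participants who missed the final in-office visit, since the electronic survey described in the SAP collected questionnaire responses.
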